### **11.3. Other Efficacy Analyses**

#### **11.3.1. Concordance Analysis of Progression-Free Survival Timings**

An assessment of the concordance between Investigator assessment of progression and IRC Assessment of progression will be provided for both arms. The calculation will be based on the percent agreement (the proportion of progression outcomes that agree or match across both IRC and Investigator Assessments).

#### **11.3.2. Number of Events of Progression During Treatment and During Follow-up**

The number and percentage of subjects with progression (based on Investigator assessment) during the treatment period and also during follow-up will be summarized for both treatment arms.

## **12. SAFETY ANALYSES**

Unless otherwise specified, all the safety analyses will be based on the Safety population as defined in Section 6 and summaries will include all events or assessments collected during the study. All the analyses will be performed by treatment arm.

The list of displays for the Safety Analyses is shown in a separate document from the RAP.

### **12.1. Extent of Exposure**

The dose (mg) and duration of exposure to ofatumumab in hours will be summarized by each infusion using summary statistics mean, standard deviation, median, minimum value, and maximum. The total number of infusions administered will also be summarised with mean, median, standard deviation, minimum, and maximum. The number and percentage of subjects who received infusions will be reported.

The frequency of infusion interruptions and incomplete infusions will also be provided.

### **12.2. Adverse Events**

All SAEs and AEs regardless of relationship to investigational product will be collected from the first dose of investigational product to 60 days after the last dose of investigational product and will be documented on the eCRF. All SAEs and AEs for subjects not receiving treatment (observation) will be collected for the same duration time (i.e. Visit 1 until 60 days after last visit, up to Visit 14). Only SAEs will be reported from 60 days after the last dose of investigational product or last treatment/observation visit to

the end of the follow-up period. All SAEs regardless of causality will be collected until the end of the follow-up period.

An overview summary of AEs, including counts and percentages of subjects with any AE, AEs related to study treatment, AEs leading to permanent discontinuation of study treatment, AE leading to dose reductions, AEs leading to dose delays/ interruptions, SAEs, SAEs related to study treatment, fatal SAEs, and fatal SAEs related to study treatment will be produced.

A summary of non-serious AEs that occurred in strictly 5% of the subjects or above will be provided (no rounding for the percentage will be used in terms of 5% threshold, e.g., event with 4.9% incidence rate should not be included in this table). The summary will be displayed by SOC and PT.

The relationship between MedDRA SOC, PT, and Verbatim Text will be displayed.

Adverse events (AEs) will be graded according to the CTCAE, Version 4.0. Adverse events will be coded to the preferred term (PT) level using the Medical Dictionary for Regulatory Affairs (MedDRA dictionary).

A summary of number and percentage of subjects with any adverse events by maximum grade will be produced. AEs will be sorted by Preferred term (PT) in descending order of total incidence. The summary will use the following algorithms for counting the subject:

- **Preferred term row:** Subjects experiencing the same AE preferred term several times with different grades will only be counted once with the maximum grade.
- **Any event row:** Each subject with at least one adverse event will be counted only once at the maximum grade no matter how many events they have.

In addition, the frequency and percentage of AEs (all grades) will be summarized and displayed in two ways: 1) in descending order of total incidence by PT only and 2) in descending order of total incidence by System Organ Classes (SOC) and PT. In the SOC row, the number of subjects with multiple events under the same system organ class will be counted once.

A separate summary will be provided for study treatment-related AEs. A study treatment-related AE is defined as an AE for which the investigator classifies the relationship to study treatment as “Yes”. A worst case scenario approach will be taken to handle missing relatedness data, i.e. the summary table will include events with the relationship to study treatment as ‘Yes’ or missing. The summary table will be displayed in descending order of total incidence by PT only.

All AEs will be listed. Additionally, a listing of subject IDs for each individual AE will be produced.

Adverse events will be summarized and listed separately during the study and up to 60 days after the last dosing.

The following adverse event tables will also be provided for events occurring from the

start of treatment until 60 days after last dosing:

- All adverse events, all serious adverse events (including deaths) for the following:
  - Secondary malignancies
  - Cardiac events
  - Small bowel Obstruction
- All infusion reactions reported as AEs, SAEs and leading to withdrawal
- All infections reported as adverse events, all serious infections reported as adverse events
- All mucocutaneous adverse events, all serious mucocutaneous adverse events
- All decreased neutrophil count/ hemoglobin count/ and platelet count adverse events, all serious decreased neutrophil count/ hemoglobin count/ and platelet count adverse events
- All autoimmune hematologic complication adverse events, all serious autoimmune hematologic complication adverse events
- All tumor lysis syndrome adverse events, all serious tumor lysis syndrome adverse events

The relationship between MedDRA SOC, PT, and Verbatim will be displayed.

Summaries based on the following covariates will be provided for all AEs:

- Gender
- Age: <70 vs. ≥70 years
- Race: White, vs. non-white.

Additionally, summaries for adverse events sorted by preferred terms (in descending order of incidence of 'Any OFA' arm) will also be provided for AE, SAE, drug-related AE, SAE, fatal AE, AE leading to permanent discontinuation of study treatment, AE leading to dose interruption/delay, mucocutaneous reaction AE, serious mucocutaneous reaction AE, autoimmune hematologic complication AE, serious autoimmune hematologic complication AE and AE by subgroup.

The following subject listings will be provided:

- Relationship of AE system organ class, preferred terms and verbatim text
- Subject numbers for individual AE (by system organ class and preferred term)
- All AEs (by preferred term and verbatim text).
- AEs leading to permanent discontinuation of study treatment
- Liver chemistry adverse events for subjects with at least one liver event.

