- Time to progression after next-line therapy

This endpoint will be defined as time (in months) from progression following randomization until progression or death following next-line therapy and counting as events deaths prior to next-line therapy. Analysis of this endpoint will only include subjects who received next-line therapy and who also had PD prior to receiving next-line therapy. Subjects with PD who died prior to receiving next-line therapy will also be included. Subjects who receive next-line therapy with a PD prior to receiving next line therapy and who do not have progression or death after next-line therapy will be censored at their last date of contact. If a subject dies prior to next-line therapy, this will count as an event. [REDACTED]

- Changes in patient reported outcome scores

Area under the curve (AUC) of change from baseline over time in the EORTC QLQ-C30, EORTC QLQ-CLL16 domain scores and total scores as well as the EQ-5D utility and VAS scores will be evaluated. Details of the methods used to evaluate changes in PRO domain and total scores will be provided in the Health Outcomes section of the RAP.

- Improvement of ECOG performance status

Improvement is defined as a decrease from baseline by at least one step on the ECOG performance status scale (improvement categorized as yes or no). The proportion of subjects with improvement will be compared between treatment groups with the Cochran-Mantel-Haenszel test adjusting for stratification factors (response at entry, number of prior treatments and type of prior treatment).

- B-symptoms/Constitutional symptoms

The proportion of subjects with no night sweats, no weight loss, no fever and no extreme fatigue will be summarized and compared to the proportion of subjects with at least one of the following: night sweats, weight loss, fever or extreme fatigue. The proportions will be compared between treatment groups with the Cochran-Mantel-Haenszel test adjusting for stratification factors (response at entry, number of prior treatments and type of prior treatment).

- Incidences of and number of subjects with grade 3 and 4 infections

The number and percentage of subjects with grade 3, 4 and 5 infections will be summarized by treatment group.

- Evaluation of myelosuppression (anemia, neutropenia, thrombocytopenia)

The number and percentage of subjects with myelosuppression will be summarized by treatment group.

- Frequency of transfusions

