## 1 Introduction

OMB157C2301 (OMB112517) is a Phase III, open-label, randomized, multicenter trial to evaluate efficacy and safety of ofatumumab (OFA) maintenance treatment versus no further treatment in subjects with relapsed chronic lymphocytic leukemia (CLL) who have responded to induction therapy using a parallel design.

**Background:** The primary endpoint has been met at the protocol-defined interim analysis that was triggered after 187 events were observed (data cut-off date on June, 19 2014). OFA maintenance demonstrated a significant improvement in PFS ( $p < 0.0001$ ) as assessed by the investigator over Obs (OFA maintenance: median [mPFS] of 29.4 months, Obs: mPFS of 15.2 months; HR 0.50; 95% CI 0.38, 0.66). A 120 day Safety update has been performed (safety update data cut-off (28-Feb-2015)).

Statistical Analyses Plan (SAP) for the current planned analysis is based on the efficacy and safety data collected up to 20-Feb-2017, the cut-off date when 280 PFS events or death occurred in the study. The analysis results will be used for descriptive purpose only. In particular supportive analysis to the primary endpoint will be provided.

All analyses that were done for the interim CSR (Dated 11-Sep-2014, Document # 2014N213614\_00) will be done for this analysis *except* the following outputs (see [Table 1](#)).

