3.1210	Summary of Frequency and Proportion of Subjects with Transfusions During the Trial
3.1220	Summary of ECG Findings at Screening
3.1222	Summary of Organ Examination Data Over Time by Investigator
3.1223	Summary of Organ Examination Data Over Time by the IRC
3.1230	Summary of Liver Chemistry Assessments for Subjects with Liver Signal/event
3.1240	Summary of Time on Treatment before Liver Event
3.1250	Summary of Subjects with Liver Chemistry Stopping Criteria for Dosing
3.1280	Summary of Blood Products and Blood Supportive Care Products
3.1282	Summary of Comparison of Grade $\geq 3$ Neutropenia Rates up to 60 Days After Last Treatment Using Modified Preferred Term
3.1283	Summary of Comparison of Grade $\geq 3$ Infection Rates up to 60 Days After Last Treatment
3.1300	Overview of Key Safety Summary by Type of Prior Treatment
3.1310	Summary of AEs with $\geq 5\%$ Incidence For all Grades and For

	Grade $\geq 3$ by Modified Preferred Term and Type of Prior Treatment
3.1320	Overview of Key Safety Summary by Number of Previous Induction Therapies
3.1340	Summary of AEs with $\geq 5\%$ Incidence For all Grades and For Grade $\geq 3$ by Modified Preferred Term and Number of Previous Induction Therapies
3.1350	Overview of Key Safety Summary by Type of Prior Chemoimmunotherapy
3.1360	Summary of AEs with $\geq 5\%$ Incidence For all Grades and For Grade $\geq 3$ by Modified Preferred Term and Type of Prior Chemoimmunotherapy
3.1370	Overview of Key Safety Summary by Response at Entry
3.1380	Summary of AEs with $\geq 5\%$ Incidence For all Grades and For Grade $\geq 3$ by Modified Preferred Term and Response at Entry
3.1390	Overview of Key Safety Summary by Age
3.1400	Summary of AEs with $\geq 5\%$ Incidence For all Grades and For Grade $\geq 3$ by Modified Preferred Term and Age
3.1410	Overview of Key Safety Summary by Gender
3.1420	Summary of AEs with $\geq 5\%$ Incidence For all Grades and For Grade $\geq 3$ by Modified Preferred Term and Gender
3.1430	Overview of Key Safety Summary by Race
3.1440	Summary of AEs with $\geq 5\%$ Incidence For all Grades and For Grade $\geq 3$ by Modified Preferred Term and Race
3.1450	Overview of Key Safety Summary by Geographic Region
3.1460	Summary of AEs with $\geq 5\%$ Incidence For all Grades and For Grade $\geq 3$ by Modified Preferred Term and Geographic Region
3.1470	Overview of Key Safety Summary by Modified RAI Stage

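### Crude AE percentages rest on a collection window tied to progression, so for non-serious events and the 60-day tables equal true rates could look up to about 20% higher (relative) on ofatumumab

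*SAP*

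**What the plan says.** SAP 12.2 (Adverse Events) and Protocol 6.4.8 set the collection rules.

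- **Ofatumumab:** all AEs are collected "from the first dose of investigational product to 60 days after the last dose of investigational product".
- **Observation:** "All SAEs and AEs for subjects not receiving treatment (observation) will be collected for the same duration time"; the window is "Visit 1 until 60 days after last visit, up to Visit 14".
- **Serious events, both arms:** "All SAEs regardless of causality will be collected until the end of the follow-up period".

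The planned measures are subject-level proportions. The AE overview gives "counts and percentages of subjects with any AE" and further categories. For the infection endpoint, SAP 11.2 says "The number and percentage of subjects with grade 3, 4 and 5 infections will be summarized by treatment group". SAP 12.4 limits an SAE summary to 60 days after the last infusion, and many listed outputs carry the same limit.

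Two outputs in the 280-event SAP (Appendix 1) and the final-analysis SAP (Table 1) are titled as comparisons between arms: Table 3.1282 for grade 3 or higher neutropenia and Table 3.1283 for grade 3 or higher "Infection Rates up to 60 Days After Last Treatment". Neither SAP defines the rate.

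Protocol 8.3.5 ends treatment at progression, unacceptable AE, withdrawal of consent or another reason. Protocol 3.1.4 moves progressed subjects to survival follow-up. The 280-event SAP reports at the interim: "OFA maintenance: median [mPFS] of 29.4 months, Obs: mPFS of 15.2 months".

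**The concern.** The non-serious AE window follows PFS, the endpoint on which the arms differ most. A subject who progresses on observation at month 9 is no longer asked about non-serious AEs after about month 11. A subject still in remission on ofatumumab is asked for about 26 months. A crude percentage counts both as one subject at risk, so part of any excess on ofatumumab may be extra time under observation and not a drug effect.

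This matters because safety compared with no further treatment is a stated secondary objective and grade 3 and 4 infection is a listed endpoint. The distortion falls on the benefit-risk reading; the primary PFS result is untouched.

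Two gaps in the SAP make the window harder to pin down. The 60-day limit is written in terms of last dosing or last infusion, which has no counterpart on observation. SAP 9.3 also ends the on-treatment period 30 days after the last dose on ofatumumab but at entry into follow-up on observation.

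**Working it through.** The documents give no figure for unequal AE observation time, so there is none to reproduce. As a check that the design medians are read as the plan reads them: 4 × (1.960 + 0.842)² / [ln(28/39.2)]² = 278 events, against the approximately 280 stated.

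**Inputs from the documents**
- Cap on the phase: 2 years (Protocol 3.1.3), taken as 24 months.
- Tail: 60 days = 60/30.4375 = 1.97 months.
- Median PFS, ofatumumab vs observation: 29.4 vs 15.2 (interim), 34.17 vs 16.89 (280 events, final-analysis SAP), 39.2 vs 28 (design).

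**Assumptions not in the documents**
- PFS is exponential, and the AE hazard is constant and equal in the two arms.
- In the base case subjects leave only through progression or death.

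**Step 1: mean window.** With median m, mean window = (m/ln 2) × [1 − exp(−24 ln 2/m)] + 1.97.
- Ofatumumab, interim: 42.4 × (1 − 0.568) + 1.97 = 18.33 + 1.97 = 20.3 months.
- Observation, interim: 21.9 × (1 − 0.335) + 1.97 = 14.59 + 1.97 = 16.6 months.

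| Medians used | Ofatumumab | Observation | Ratio |
|---|---|---|---|
| Interim | 20.3 | 16.6 | 1.23 |
| 280 events | 21.0 | 17.2 | 1.22 |
| Design | 21.5 | 20.1 | 1.07 |

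The gap is about 3.7 months with the observed medians and 1.5 months with the design medians. A 96-week cap (22.1 months) lowers the interim ratio to 1.21. If no dose is given at the progression visit, the last dose is about 8 weeks earlier and the ofatumumab window ends about 4 days after progression; the interim ratio is then 1.18.

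**Step 2: crude percentage under an equal hazard h.** With λ = ln 2/m, the percentage is 1 − exp(−1.97h) × {λ/(λ+h) × [1 − exp(−24(λ+h))] + exp(−24(λ+h))}. At h = 0.02 per month with the interim medians this gives 32.5% vs 27.1%, ratio 1.20. For h from 0.01 to 0.05 the ratio runs from 1.21 to 1.16.

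By how common the event is:

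| Medians used | Observation | Ofatumumab | Ratio |
|---|---|---|---|
| Interim | 10% | 12.2% | 1.22 |
| Interim | 30% | 35.8% | 1.19 |
| Interim | 50% | 58.3% | 1.17 |
| Interim | 85% | 91.0% | 1.07 |
| 280 events | 10% | 12.1% | 1.21 |
| Design | 10% | 10.7% | 1.07 |

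**Step 3: discontinuation for other reasons.** The documents give no such rate. Suppose a proportion d of ofatumumab subjects would stop by 24 months for reasons other than progression (added hazard −ln(1−d)/24), and none do on observation. The interim mean window on ofatumumab becomes 19.45, 18.57, 17.65 and 16.67 months for d = 10, 20, 30 and 40%. Divided by 16.56, the ratios are 1.175, 1.121, 1.066 and 1.006.

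**Step 4: the alternative measure.** A first-event rate per unit of person-time has an expected ratio of 1.00 under equal constant hazards, whatever the windows.

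**The case against.** Much of the opposing case stands.

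- **Serious events.** A reader might infer that every AE, SAE and infection summary is distorted. The documents do not support that. SAEs are collected to the end of follow-up in both arms, SAP 12 includes all events collected unless otherwise specified, and SAP 12.3 pools treatment and follow-up for infections. Whole-study SAE, fatal-event and serious-infection tables (for example 3.0320, 3.0420 and 3.0550) are therefore not subject to this cut-off.
- **Size.** A reader might take 20% as the expected excess. It is near the top of the range. It needs the observed medians, events that are not very common, and no exit except progression or death. Protocol 8.3.5 names other exits, and on ofatumumab each closes the window. Such exits on observation would partly offset this.
- **The two comparison tables.** It cannot be shown that 3.1282 and 3.1283 use crude percentages; only their titles are available.
- **Descriptive use.** The 280-event and final-analysis SAPs call their results descriptive. They list treatment duration (3.0062), duration of follow-up (1.4230) and SAEs before or after next therapy (3.0929). These help show unequal time but do not adjust any AE percentage for it.
- **Person-time is not neutral.** It assumes a roughly constant hazard. Protocol 6.4.6 notes that infusion reactions cluster in the first two infusions, and they cannot occur on observation. Dividing early events by the longer ofatumumab person-time could dilute real harm.

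None of this supplies an adjusted comparison for non-serious events or the 60-day tables. An unknown discontinuation rate is itself a reason to use the actual windows.

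**Conclusion.** The point holds for non-serious AEs and for all tables limited to 60 days after last treatment, including the SAE and serious-infection versions of those tables. Under equal true rates, crude percentages could look up to about 20% higher (relative) on ofatumumab with the observed medians. The excess is about 7% with the design medians or at an observation incidence near 85%. It is close to nothing if about 40% of ofatumumab subjects stop for other reasons.

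These figures rest on exponential PFS, a constant equal hazard, a 24-month cap, and the reading that scheduled observation visits end at progression. The direction is against ofatumumab in the base case, but it is not guaranteed: 40% other discontinuation together with the earlier last-dose anchor gives an interim window ratio of 0.968. Nor do the figures support saying that observation subjects leave collection much earlier; the mean difference is about 3.7 months in a maximum window of about 26.

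The change should be made: the comparison is a stated objective and the needed data are already collected.

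**What to change.** Keep the planned percentages and add the following.

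1. For AEs, grade 3 or higher AEs, infections and neutropenia within the 60-day window, give subjects with a first event per 100 patient-years, with a rate ratio and 95% CI. Cumulative incidence by arm is an acceptable alternative where the hazard is clearly not constant.
2. Report infusion reactions separately so that early events on one arm are not diluted.
3. Define the rate in Tables 3.1282 and 3.1283 on the same basis.
4. State the end-of-window anchor for observation subjects wherever the text says last dose, dosing or infusion, and reconcile it with the on-treatment definition in SAP 9.3.
5. Tabulate the length of the collection window by arm.
6. If SAEs are also expressed as rates over the whole study, use person-time to the end of SAE follow-up, not the 60-day window.

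The cost is a few extra table columns and one added definition; no new data are needed. The downside is the constant-hazard assumption behind person-time rates, which is why the percentages stay and cumulative incidence is offered.

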### 12.3. Adverse Events of Special Interest

A comprehensive list of MedDRA terms based on clinical review will be used to identify each type of events. Changes to the MedDRA dictionary may occur between the start of the study and the time of reporting and/or emerging data from on-going studies may highlight additional adverse events of special interest, therefore the list of terms to be used for each event of interest and the specific events of interest will be based on the safety review team (SRT) agreements in place at the time of reporting.

The events of special interest include

- Infusion related AEs
- Infections
- Mucocutaneous reactions
- AEs associated with decreased neutrophil, hemoglobin or platelet count
- Prolonged and late-onset neutropenia
- Autoimmune Hematologic Complication Adverse Events
- Tumor Lysis Syndrome (TLS)

Summaries of the number and percentage of subjects with these events will be provided for each type of event separately.

#### **Infusion related AEs**

Infusion reactions will be summarized using the preferred terms from the AE dataset.

The process for defining and reporting the infusion reactions is the following:

#### 1) Select the candidate AEs

For each infusion, only AEs occur during and within 24 hours following the end of infusion will be included as candidate AEs.

If the AE onset date is available but the onset time is missing, then the AE will be included if it occurs on the same day as the infusion and the day following the infusion.

2) The list of candidate events based on the above criteria will be reviewed by the GSK clinical and safety review team to select the final set of terms for inclusion in the analysis tables. This will be conducted at the Preferred Term (PT) level.

